15.0 Risks to Participants*

15.1 This study involves no greater than minimal risk to the subjects enrolled. BUS is a noninvasive imaging tool currently used in standard of care procedures for premature infants in the NICU. It has no radiation, does not require infants to fast or any other special preparation before the procedure, and is well-tolerated even by sick infants.

16.0 Potential Benefits*

16.1 There may be no direct benefit to the patient in the study. However, the BUS imaging done as part of the study will be available to any treating physician and may be helpful in medical management of the patient.

16.2 Knowledge gained from this study can potentially benefit future infants with NEC concern by providing strong evidence regarding the optimal use of BUS for NEC evaluation that is both safe and effective.

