Specific aim #2: To determine the capability of implementing BUS for NEC evaluation in a level III NICU within an adult hospital. We hypothesize that BUS timeliness, quality, and inter-rater reliability are comparable between level III and IV NICUs.

The addition of BUS to the diagnostic repertoire of infants with suspected NEC is an important contribution to neonatology. Before widespread adoption can be realized, however, strong evidence is needed to determine whether the addition of BUS would lead to actual clinical benefits, including in level III NICUs in adult hospitals. We anticipate that our study will help address this critical gap in knowledge and provide important insights as to the safe and effective use of BUS for NEC.

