27.0 Adverse Events and Unanticipated Problems*

27.1 Monitoring: The study team will meet bi-weekly to monitor study progress, review participants and data, and troubleshoot any questions or problems related to the study. As all study interventions are standard of care, we do not anticipate any adverse events or problems related to the study protocol or add-on BUS.

27.2 Reporting: We confirm that Policy 5.11 Reportable Events of the CM Research Program Policies and Procedures will be followed in regard to reporting adverse events and other unanticipated problems to the CM IRB.

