28.0 Statistical Analysis*

28.1 We will use two-tailed McNemar's test with paired measures to analyze differences in diagnostic thinking efficacy and therapeutic efficacy from pre- and post-BUS surveys. Comparison of duration of antibiotics, bowel rest, and days to full enteral feeds will be performed using Student's t-test. Kaplan-Meier curve will be used to analyze time to full feeds between the 2 groups, censoring for death, discharge/transfer out of the hospital, or 30 days following initial NEC concern. Analyses of patient outcomes (duration of bowel rest, duration of antibiotics, time to full feeds) will follow the intention-to-treat principle, with statistical significance set at a P value of < 0.05.

28.2 We will use t-test to analyze differences in mean time of BUS image acquisition and reporting. Chi-square test will be used to compare differences in proportion of BUS studies that were performed and reported per standardized protocol. Inter-rater reliability for BUS studies will be assessed by Cohen's kappa statistics.

28.3 Sample size was calculated based on our pilot study which demonstrated a mean \pm SD of duration to full enteral feeds of 16 ± 9 days per episode of NEC concern. Using this information, we generated Table 1, which shows sample sizes for a range of possible means and standard deviations, with significance level of 0.05 and 80% power. For a 1-year study with 67 to 81 distinct episodes, for an SD of +8 days, we anticipate having sufficient sample size to detect a 5- to 6-day difference in mean duration to full feeds (highlighted in gray in Table 1).

Difference of means between groups	Expected Standard Deviation		
	± 8	± 9	± 10
4 days	126	160	198
5 days	81	102	126
6 days	56	72	88

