30.0 Storing of Data and/or Banking of Specimens for Future Research

30.1 If this study involves storing of data or banking of leftover specimens for future research, indicate how the use will be managed:

Contributing data and/or leftover specimens to an existing CM repository protocol (myIRB# _____)

Contributing data and/or leftover specimens to an existing non-CM repository (Institution/Repository Name: _____)

Not contributing to an existing repository for the management of data/specimens for future research use.

Other:

30.2 If not contributing to an existing repository, describe:

- To maximize potential impact, de-identified clinical and imaging data collected from the study will be stored for potential use for future research.
- De-identified data will be archived in Redcap and will be housed within the CMH Data Center by the Division of Biomedical Informatics as described before in section 23 (HIPPA) and section 29 (Data management).
- Data will be accessed through Redcap. Access will be restricted to only those persons specifically granted authorization by the Principal Investigator.
- Data will be stored for at least five years after final publication of study results.
- A formal request for release of de-identified data will be required, preferably by e-mail. Approval for release will be by the Principal Investigator. Both CM researchers and external researchers can request access for the data. Only de-identified data will be available.

31.0 Provisions to Monitor the Data to Ensure the Safety of Participants – NA (no more than minimal risk research)

STUDY MANAGEMENT

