32.0 Setting & Locations*

32.1 The NICU at CMKC is an 87-bed level IV NICU. Majority of infants admitted at the NICU are born at other hospitals and are typically transferred to CMKC due to need for specialized care. Neonatologists are in-house 24/7. As a children's hospital, radiology staff at CMKC are composed of pediatric sonographers and pediatric radiologists. BUS for NEC evaluation has been available at CMKC since 2015. Despite its availability, current use of BUS for NEC evaluation at CMKC remains highly variable, often dependent upon the individual preferences of the treating neonatologist.

32.2 The NICU at KUMC is a 32-bed level III NICU. Majority of infants admitted at the NICU are born at KUMC. Neonatology coverage at KUMC is provided by CMKC neonatologists who are also in-house 24/7. As a general adult hospital, radiology staff at KUMC are composed primarily of adult sonographers and adult radiologists. Currently, only one radiologist at KUMC has the expertise to perform BUS for NEC evaluation. Because of this limited availability, BUS for NEC evaluation is infrequently performed at KUMC. However, as part of our study's aim of investigating

generalizability of BUS in NICUs of adult hospitals, pre-study training will be done to standardize performance and availability of BUS between CMKC and KUMC.

32.3 Close research collaboration exists between the NICUs of CMKC and KUMC. Several research protocols done at CMKC are also done at KUMC. In fact, KUMC is such an active site for collaborative research that a CMKC-employed neonatology research coordinator ([name]) is dedicated solely for recruitment of participants at KUMC-NICU. Although KUMC has its own IRB, majority of the research done at KUMC NICU is approved via reliance on the IRB at CMKC.

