
The research could not practicably be carried out without the requested waiver/alteration (i.e., explain why the study could not be done if permission/assent/consent were required)
	
We initially conducted a pilot study to determine the feasibility of a RCT study design of BUS for NEC evaluation. While the RCT study design itself was feasible, we found that the process of obtaining consent was not practicable. The reasons why the proposed research could not be practicably carried out without the requested waiver are detailed below and in Fig 3:
 
(1) NEC is an emergency, making traditional parental consent at time of NEC concern impossible. Because NEC can rapidly deteriorate, infants with suspected NEC require “stat” evaluation with imaging and other laboratory tests. Families approached for research during emergency situations are often unable to give proper informed consent because of physical and emotional distress. Obtaining consent at time of NEC concern would also increase the risk of delaying evaluation. For these reasons, traditional parental informed consent at time of NEC concern is not possible for our study.
 
(2) Obtaining consent prior to NEC concern will require impractically large numbers to meet sample size demands. To overcome the emergency nature of NEC, we elected in our pilot study to seek consent from all infants who meet eligibility criteria, follow consented infants over time, and randomize only consented infants who develop concern for NEC. The problem with this approach is that only 36% (20/56) of consented infants developed NEC concern for randomization into the study. Based on these numbers, we will need to successfully consent 222 infants to achieve our target sample size of 80 infants. Although mathematically possible, it would require implausibly high approach and consent rates to successfully enroll 222 infants over the 2 years of the proposed study, making this approach of obtaining consent prior to NEC concern impracticable. This approach would also intrude on many families who would not need and may not

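### Surgery is not compared by arm and death enters only as censoring, so an excess of either could go unreported while treatment durations look favourable

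*Combined protocol and SAP*

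**What the plan says.** **Aims and benefit statements.** Aim 1 (sections 1.0 and 2.1) concerns the impact of add-on BUS on patient outcomes. Section 16.2 says the knowledge gained may help future infants by "providing strong evidence regarding the optimal use of BUS for NEC evaluation that is both safe and effective". The end of section 1.0 anticipates that the study will "provide important insights as to the safe and effective use of BUS for NEC".

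**Analysis by arm.** Section 28.1 names three patient outcomes for intention-to-treat analysis: duration of bowel rest, duration of antibiotics, and time to full feeds. Death appears there once, as a reason for censoring the Kaplan-Meier curve.

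**Imaging times.** Section 28.2 states: "We will use t-test to analyze differences in mean time of BUS image acquisition and reporting". Aim 2 in section 1.0 ties timeliness to level III versus level IV units, so this is a comparison between sites within BUS studies, not between arms.

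**Data collected.** Section 26.1 lists order, acquisition and reporting times for both imaging tests, and surgical treatment by drainage or laparotomy. Section 24.2 includes the date of death among the recorded items.

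**Withdrawal.** Section 25.1 allows withdrawal after transfer to another hospital, or after laparotomy with ostomy and mucus fistula. Section 25.3 then stops new data collection, except for adverse events and other safety matters.

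**Expected harm.** Section 27.1 says: "As all study interventions are standard of care, we do not anticipate any adverse events or problems related to the study protocol or add-on BUS". Section 32.2 says of the second site: "Because of this limited availability, BUS for NEC evaluation is infrequently performed at KUMC".

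**The concern.** The three analysed outcomes are all durations, and durations are easily distorted by the events that are not analysed. An infant who dies early may contribute a short antibiotic course or bowel rest, and never reaches full feeds. Section 28.1 does not say how such an infant enters the t-tests. An infant withdrawn after laparotomy with ostomy may stop contributing feeding data, because 25.3 limits what is collected afterwards. Intention-to-treat analysis does not recover values that were never recorded.

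If one arm had more surgery or more deaths, its mean durations could shorten or lose their longest values, and nothing in section 28 would show why. Surgery and death are also patient outcomes in their own right under Aim 1. Readers who see favourable durations beside the wording of 16.2 could take the result as reassurance on safety that the analysis does not supply.

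**Working it through.** **1. What the sample size covers.** The formula is total N = 4 × [SD × (1.960 + 0.842) / difference]². For SD 8 and a 5-day difference, N = 4 × [8 × 2.802 / 5]² = 80.4, against 81 in Table 1. The other cells reproduce to within rounding as total N, two-sided 0.05, 80% power and equal allocation. Table 1 therefore sizes days to full feeds only. No size is given for surgery or death.

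**2. Number of infants.** Addendum B uses a target of 80 infants and section 8.0 an enrollment goal of 200 neonates. Section 28.3 counts 67 to 81 episodes. I use 40 and 100 infants per arm, assuming equal allocation.

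**3. Precision for a difference in proportions.** The documents give no surgery or death rate. I assume 10% in both arms, with 5% and 20% as the range. The Newcombe interval uses the Wilson limits L and U of each arm. With equal observed rates p its half-width is √[(p − L)² + (U − p)²].

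- 4/40: L = 0.0396, U = 0.2305. Half-width = √[0.0604² + 0.1305²] = 0.144, or 14.4 points.
- 10/100: L = 0.0552, U = 0.1744. Half-width = √[0.0448² + 0.0744²] = 0.087, or 8.7 points.

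| Assumed rate | 40 per arm | 100 per arm |
|---|---|---|
| 5% | 12.1 points (L 0.014, U 0.165) | 6.8 points (L 0.022, U 0.112) |
| 10% | 14.4 points | 8.7 points |
| 20% | 17.6 points (L 0.105, U 0.348) | 11.1 points (L 0.133, U 0.289) |

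**4. Zero events in one arm.** The exact two-sided 95% upper limit is 1 − 0.025^(1/n). This gives 8.8% for n = 40 and 3.6% for n = 100. The one-sided 95% bound, 1 − 0.05^(1/n), gives 7.2% and 3.0%.

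**5. Power for a doubling from 10% to 20%.** With a pooled null variance, power = Φ{[0.10√n − 1.960√(2 × 0.15 × 0.85)] / √(0.09 + 0.16)}.

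- n = 40: (0.632 − 0.990) / 0.5 = −0.71, power 24%.
- n = 100: (1.000 − 0.990) / 0.5 = 0.02, power 51%.
- For 80% power: n = (0.990 + 0.842 × 0.5)² / 0.10² ≈ 199 per arm.

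These figures treat infants as independent. Section 10.2 assigns the arm by month of birth, so any similarity among infants born in the same month would widen the intervals.

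**The case against.** **A reader might infer that the plan promises to prove BUS safe.** It does not. Section 16.2 is a conditional statement under potential benefits, section 1.0 only anticipates insights, and neither aim nor the hypothesis in 2.2 names safety. What stands is that the wording calls the evidence strong, and the design cannot deliver that for safety.

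**A reader might infer that safety oversight is absent,** from "Provisions to Monitor the Data to Ensure the Safety of Participants – NA" in section 31.0. That entry covers one section and gives minimal risk as its reason. Section 27 keeps bi-weekly review by the study team and adverse-event reporting to the IRB, and 25.3 keeps safety information after withdrawal. Trial monitoring is also a separate question from which outcomes are analysed.

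**A reader might infer that add-on BUS delays decisions,** because Addendum B rejects consent at the time of concern partly on the ground that "Obtaining consent at time of NEC concern would also increase the risk of delaying evaluation". That sentence is about a consent process. Nothing tells clinicians to wait for BUS: radiographs follow the usual workflow in both arms (10.3), and treatment stays with the neonatologist (10.8). Time to the last assigned image would be longer with two tests by construction and would not measure harm. Time of treatment decision is not among the items listed in 26.1.

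**A reader might infer that BUS performance at the second site goes unexamined.** Section 32.2 plans training before the study, and Aim 2 with 28.2 examines timeliness, adherence to the imaging protocol and inter-rater reliability.

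**Surgery is an ambiguous outcome and the estimates will be imprecise.** Both are true. Earlier detection could raise the surgery rate without harm, which is a reason to report death beside it. Imprecision is a reason to show an interval rather than to omit the outcome.

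**Conclusion.** The point holds as a gap in section 28.1, not as a failure of oversight. Surgery and death bear directly on Aim 1, yet neither is compared by arm. Together with the withdrawal rule and the censoring of deaths, this leaves the three duration outcomes open to a favourable reading that the unreported events might contradict.

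The size of the gap is one of precision. Under an assumed 10% rate in both arms, the trial could estimate a difference in surgery to about ±14 points at 40 per arm or ±9 points at 100 per arm. Over assumed rates of 5% to 20% the range is 12 to 18 points and 7 to 11 points. Zero events would still leave an upper limit of 8.8% or 3.6%. These figures rest on assumed rates, equal arms and independent infants. They support describing surgery and death with intervals; they do not support calling the safety evidence strong. The documents contain nothing to suggest that BUS is harmful or that an excess is expected.

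**What to change.** 1. **Section 28.1.** Add, by assigned arm under intention-to-treat and counted per infant, the proportion with peritoneal drainage or laparotomy and the proportion who die before NICU discharge, each with a 95% CI for the difference. Figures by site should be descriptive only.
2. **Sections 25.1 and 25.3.** State that withdrawn infants stay in these two analyses, and that surgery and death count as safety information under 25.3. Report by arm how many infants were transferred out with later status unknown.
3. **Section 26.1.** Name death in the data list, to match 24.2.
4. **Sections 16.2 and 1.0.** Replace the claim of strong safety evidence with the size of excess that the trial can exclude, and say which sample size applies.
5. **Optional.** Describe by arm the time from first order to radiograph report, which is like for like. Describe separately the added time to the BUS report in the AXR + BUS arm, without treating it as a harm.
6. **Section 27.1.** Reconcile its description of all study interventions as standard care with section 1.0, which calls radiographs the standard modality where BUS is scarce, and with the account of the second site in 32.2.

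The cost is wording and two short tables. Imaging times, surgical treatment and date of death are already recorded, and no visits or infants are added. The downside is a narrower safety statement.

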17.0 Investigator Assessment of Risk/Benefits Ratio*

17.1

Select as applicable:	Pediatric Risk Category:	
	Category 1	Research not involving greater than minimal risk (45 CFR §46.404 and 21 CFR §50.51)
	Category 2	Research involving greater than minimal risk but presenting the prospect of direct benefit to the individual participants. (45 CFR §46.405 and 21 CFR §50.52)
	Category 3	Research involving greater than minimal risk and no prospect of direct benefit to individual participants, but likely to yield generalizable knowledge about the participant's disorder or condition. (45 CFR §46.406 and 21 CFR §50.53)
	Category 4	Research not otherwise approvable which presents an opportunity to understand, prevent, or alleviate a serious problem affecting the health or welfare of children. (45 CFR §46.407 and 21 CFR §50.54)
Select if applicable:	Adult Risk Category:	
	Not Greater than Minimal Risk	
	Greater than Minimal Risk	

18.0 Payment, Reimbursement and Tangible Property provided to participants*

Is payment, reimbursement, or tangible property part of the study?

Yes No (*If No, delete the following subsections*)

19.0 Compensation for Research-Related Injury - NA

20.0 Economic Burden to Participants

20.1 There will be no economic burden to participants of the study. All BUS imaging done as part of the study will be paid for by the study and will not be billed to participants.

21.0 Parental Permission and Adult Consent Process*

Written Informed Permission/Consent

Written informed permission of parent/LAR for pediatric participants

Study group(s) to which this method applies:

Written informed consent of adult participants

Study group(s) to which this method applies:

Written informed consent of participants turning 18

This includes the continued access to and use of their PHI by the study team.

Study group(s) to which this method applies:

Waiver of Documentation of Permission/Consent

Permission/Consent form provided but signature will **NOT** be obtained (e.g. verbal consent)

Must complete **Addendum A: Waiver of Documentation of Permission/Consent**

Waiver of written documentation of permission of parent/LAR for pediatric participants

Study group(s) to which this method applies:

Waiver of written documentation of consent of adult participants

Study group(s) to which this method applies: Neonatologists taking part of the survey

Waiver of written documentation of consent of participants turning 18

Study group(s) to which this method applies:

Waiver or Alteration of Permission/Consent

Parent/LAR permission/adult consent will **NOT** be obtained, or an alteration to an element(s) of consent.

Must complete [Addendum B: Waiver of Permission/Assent/Consent](#)

Waiver/Alteration of permission of parent/LAR for pediatric participants

Study group(s) to which this method applies: AXR group and AXR + BUS group

Waiver/Alteration of consent of adult participants

Study group(s) to which this method applies:

Waiver/Alteration of consent of participants turning 18

Study group(s) to which this method applies:

Additional Methods

Obtaining permission/assent/consent of non-English speaking parents or participants

Must compete [Addendum C: Non-English Speaking Participants](#)

Study group(s) to which this method applies:

Surrogate decision maker consent to be used when adults are not capable of consenting for themselves

Must complete [Addendum D: Surrogate Decision Maker Consent](#)

Study group(s) to which this method applies:

22.0 Assent of Pediatric Participants

22.1 Select the option(s) that apply to the study:

Assent of pediatric participants WILL BE SOUGHT following assessment of ability to assent.

Obtaining assent of pediatric participants is NOT POSSIBLE due to:

The capability of the participants (considering the ages, maturity, physical and/or psychological state) is so limited that they cannot reasonably be consulted.

The intervention or procedure involved in the research holds out a prospect of direct benefit that is important to the health or well-being of the participants and is available only in the context of the research.

Obtaining assent of pediatric participants is NOT PRACTICLE given the context of this study (e.g., minimal risk, no direct contact with participants).
Must complete Addendum B: Waiver/Alteration of Permission/Accent/Consent

23.0 HIPAA and Confidentiality

23.1 HIPAA Authorization

Full Written HIPAA Authorization will be obtained (within the p/a/c form or standalone form)

Partial Waiver of HIPAA Authorization (e.g. waiver for recruitment and pre-screening purposes only)

Must complete Addendum E: Waiver/Alteration of HIPAA Authorization

a) Describe what PHI must be accessed for recruitment/pre-screening purposes prior to obtaining HIPAA Authorization.

Alteration of HIPAA Authorization (some but not all required elements of an Authorization are present, e.g. signature will not be obtained)

Must complete Addendum E: Waiver/Alteration of HIPAA Authorization

a) Describe which proposed elements to be altered.

Waiver of HIPAA Authorization (authorization will NOT be obtained)

If Other, explain:

23.2 Specify the PHI for which accessing (“viewing”) or recording (“writing down”) is necessary for the purpose of this research:

1. Name/Initials	 Accessed only	 Recorded
2. All elements of date (except year) directly related to an individual (e.g. date of birth, admission date, discharge date, date of death)	 Accessed only	 Recorded
3. Medical record number	 Accessed only	 Recorded
4. Account number	 Accessed only	 Recorded
5. Health plan identification number	 Accessed only	 Recorded
6. Social Security Number	 Accessed only	 Recorded

SHORT TITLE: BUS for NEC

7. Device identifiers and serial number	 Accessed only	 Recorded
8. Certificate/License number	 Accessed only	 Recorded
9. Telephone number	 Accessed only	 Recorded
10. Fax number	 Accessed only	 Recorded
11. Email addresses	 Accessed only	 Recorded
12. Web addresses (URLs); Internet IP addresses	 Accessed only	 Recorded
13. Street address, city, county, precinct, zip code or equivalent geographical codes	 Accessed only	 Recorded
14. Full face photographic images and any comparable images	 Accessed only	 Recorded
15. Biometric identifiers, including finger and voice print	 Accessed only	 Recorded
16. Vehicle identifiers and serial numbers, including license plate number	 Accessed only	 Recorded
17. Any other unique identifying number, characteristic or code that may help identify individual participants including their initials (e.g. student or employee ID number)	 Accessed only	 Recorded
18. Elements of date, including year, for persons 90 years or older	 Accessed only	 Recorded
19. Other:	 Accessed only	 Recorded

23.3 Patient information will be maintained in a REDCap application and will be housed within the CMH Data Center by the Division of Biomedical Informatics. The hosting server has an internal failover two-node cluster. The CMH Data Center is constantly staffed by qualified personnel and physical access is limited to authorized personnel. The Center has optimized conditions for the servers and stabilized electrical supply. The database has a full backup. The database server is located inside the CMH corporate firewall. A person must have CMH system access to login.

23.4 Additional security for the study patient database restricts access to only those persons specifically granted authorization by the Principle Investigator. It is possible for data to be downloaded from REDCap. Individuals who lack authority to see confidential data can download reports with non-identifiable data only. The core research group will have the ability to download sensitive fields and if such a download occurs, REDCap maintains a record of who, what, when, and to where copies of the database were imported.

23.5 A Certificate of Confidentiality has not been issued for this study.

